## 5.2.2. Analyses for Continuous Data

Unless otherwise specified, descriptive statistics for continuous variables are n, mean, median, standard deviation, minimum, and maximum.

The CI for the mean of the continuous variable will be constructed by the standard method based on the Student t distribution.

#### 5.2.2.1. Geometric Means

Continuous immunogenicity endpoints will be logarithmically transformed for analysis. Geometric means and the associated 2-sided 95% CIs will be derived by calculating group means and CIs on the natural log scale, based on the Student t distribution, and then exponentiating the results.

#### 5.2.2.2. Geometric Mean Fold Rises

GMFRs will be calculated as the group mean of the difference of logarithm-transformed assay results (later time point minus earlier time point) and exponentiating the mean. GMFRs are limited to participants with nonmissing values at both time points. The associated 2-sided 95% CIs will be obtained by constructing CIs using the Student t distribution for the mean difference on the logarithm scale and exponentiating the confidence limits.

#### 5.2.2.3. Reverse Cumulative Distribution Curves

Empirical RCDCs will plot proportions of participants with values equal to or exceeding a specified assay value versus the indicated assay value, for all observed assay values. Data points will be joined by a step function with the line first going down and then to the right to the next assay value.

## 5.3. Methods to Manage Missing Data

#### 5.3.1. Safety Data

Standard algorithms for handling missing AE dates and missing AE severity will be applied as described in the safety rulebook summary.

Missing data handling rules on the safety data are described in detail in the corresponding endpoint sections.

#### 5.3.1.1. Reactogenicity Data

For derived variables based on the reactogenicity data, if any day of the 7-day e-diary is available, the "any day (Days 1-7)" data will be considered nonmissing.

The reactogenicity data are collected in the e-diary, which does not allow participants to skip any questions. Therefore, for a specific day, if the e-diary data are transferred for that day, all of the reactogenicity data for the participant on that day are nonmissing. In general, for any participant with all 7 days of the e-diary data missing, this participant will not be included in the analysis (ie, assuming MCAR). If only 1 through 6 days of e-diary data are transferred, it is expected that any missed reactogenicity events would be entered in the AE CRF if any experienced reactogenicity was not reported in the e-diary due to missed days. Therefore, the primary analysis will use reactogenicity recorded in the AE CRF to impute the partially missed e-diary data to estimate the reactogenicity rate during the e-diary collection period. The AE CRF is designed as a log page, which means only events that occurred will be recorded and events that did not occur will not be recorded. Therefore, all remaining missing days are considered as "no." This imputation can reasonably estimate the reactogenicity event rates during the e-diary collection period.

## 5.3.2. Immunogenicity Data

Any assays above LLOQ are considered accurate, and their quantitated values will be reported. Values below the LLOQ, or denoted as BLQ, will be set to  $0.5 \times \text{LLOQ}$  for analysis.

For calculating a fold rise, < LLOQ will be converted to  $0.5 \times$  LLOQ for a numerator, and < LLOQ will be converted to LLOQ for a denominator when only 1 of either the numerator or denominator is < LLOQ. If both the numerator and denominator are < LLOQ, then both will be converted in the same way.

The LLOQs for each assay will be included in the final released assay data.

Values for sera that are designated as QNS, indeterminate results, or values recorded as "not done" will be set to "missing." Additionally, any time point with no blood draws will not be included in the analysis. No imputation will be done for these missing values, as MCAR is assumed for immunogenicity data according to Scott and Hsu.

## 6. ANALYSES AND SUMMARIES

#### 6.1. Primary Endpoint(s)

## 6.1.1. Local Reactions and Systemic Events

Reactogenicity data will be summarized for each of the 6 age/risk/dose-level groups (Section 2.2.1.1.1). Data will be summarized by vaccine group, according to the study interventions the participants actually received.

#### 6.1.1.1. Main Analysis

- Estimand strategy: Treatment policy (Section 2.2.1.1.1).
- Intercurrent events and missing data: All data collected are included; partially missing e-diary data are imputed as "no" (Section 5.3.1.1); e-diary data that are confirmed as errors will not be used for analysis.
- Analysis set: Safety population (only participants with at least 1-day e-diary data transferred are included in the calculation) (Section 4).
- Analysis methodology: 95% CI of the proportion of participants reporting each event will be calculated using the Clopper-Pearson method (Section 5.2.1).
- Analysis timing: At primary analyses (when all primary endpoint data are available).
- Descriptive statistics, including the proportion (%), the numerator (n) and the denominator (N) used in the proportion calculation, and the 95% CI for percentage using the Clopper-Pearson method, will be presented for each group (Section 5.2.1).
- Bar charts with the proportions of participants for each and any local reaction and each and any systemic event throughout the 7 days will be plotted for each group. The bars will be divided into severity categories to highlight the proportions of participants by maximum severity.

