8.3.4. Reactogenicity Electronic Diary

The participant or participant's parent(s)/legal guardian will be required to complete a reactogenicity e-diary after each vaccination. These participants or participants' parent(s)/legal guardians will be asked to monitor and record local reactions, systemic events, and temperature for 7 days from the day of administration of the study intervention. The reactogenicity e-diary allows recording of these assessments only within a fixed time window, thus providing an accurate representation of the participant's experience at that time. Data on local reactions and systemic events reported in the reactogenicity e-diary will be transferred electronically to a third-party vendor, where they will be continually available for review by investigators, Pfizer clinicians, and other selected study team members via an internet-based portal.

At intervals agreed to by the vendor and Pfizer, these data will be transferred electronically into Pfizer's database for analysis and reporting. These data do not need to be reported by the investigator in the CRF as AEs.

Investigators (or designee) will be required to review the reactogenicity e-diary data online at frequent intervals as part of the ongoing safety review.

The investigator or designee must obtain stop dates from the participant or participant's parent(s)/legal guardian for any reactions ongoing on the last day that the reactogenicity e-diary was completed. The stop dates should be documented in the source documents and the information entered in the CRF.

Please note that all provisioned e-diary devices must be collected at the end of Visit 3 (1-month follow-up visit) per the SoA.

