If a participant or participant's parent(s)/legal guardian reports redness or swelling >14 caliper units (or >7 cm) for participants <12 years of age and >20 caliper units (or >10 cm) for participants ≥12 years of age or a Grade 3 local reaction (Table 2), any Grade 3 systemic event (Table 3), or fever >39.0°C (102.1°F) (Table 4) in the reactogenicity e-diary, a telephone contact should occur to ascertain further details and determine whether a site visit is clinically indicated. If suspected Grade 4 local reaction (Table 2), systemic event (Table 3), or fever >40.0°C (>104.0°F) (Table 4) is reported in the reactogenicity e-diary, a telephone contact or site visit should occur to confirm whether the event meets the criteria for Grade 4. A site visit must be scheduled as soon as possible to assess the participant unless any of the following is true:

- The participant is unable to attend the unscheduled visit.
- The local reaction/systemic event is no longer present at the time of the telephone contact.
- The participant or participant's parent(s)/legal guardian recorded an incorrect value in the reactogenicity e-diary (confirmation of a reactogenicity e-diary data entry error).
- The PI or authorized designee determined it was not needed.
- This telephone contact (or site visit) will be recorded in the participant's source documentation and the CRF.

If the participant is unable to attend the unscheduled visit, or the PI or authorized designee determined it was not needed, any ongoing local reactions/systemic events must be assessed at the next study visit.

During the unscheduled visit, the reactions should be assessed by the investigator or a medically qualified member of the study staff such as a study physician or a study nurse, as applicable to the investigator's local practice, who will:

- Measure body temperature (°F/°C).
- Measure minimum and maximum diameters of redness (if present).
- Measure minimum and maximum diameters of swelling (if present).
- Assess injection site pain (if present) in accordance with the grades provided in Table 2.
- Assess systemic events (if present) in accordance with the grades provided in Table 3.
- Assess for other findings associated with the reaction and record on the AE page of the CRF, if appropriate.
- The investigator or an authorized designee will complete the unscheduled visit assessment page of the CRF.

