# 3. ENDPOINTS AND BASELINE VARIABLES: DEFINITIONS AND CONVENTIONS

## 3.1. Primary Endpoint(s)

#### 3.1.1. Primary Safety Endpoints

Primary safety endpoints include both reactogenicity data collected from the e-diary and AE data collected from the CRF.

Based on feedback from the FDA on multiple vaccine programs, reactogenicity data will utilize both e-diary data (prompted local reactions and systemic events) and reactogenicity events (related or unrelated) reported in the AE CRF during the e-diary collection period. Since the AE CRF does not designate a specific page to collect reactogenicity data for an untransmitted e-diary, Pfizer has adopted a process of providing a listing of AEs reported within 7 days after vaccination to the clinical team to review and determine ("flag") which

PTs should be considered reactogenicity events before the database lock. AEs reported on the same day of vaccination but missing a start time are defaulted to AEs reported after vaccination. Following these review steps, those AEs reported within 7 days after vaccination that match flagged PTs (either related or unrelated) will be considered reactogenicity data. If the same reactogenicity event is reported on the same day from both the e-diary and the AE CRF, the highest grade from the 2 data sources will be used for that specific day for analysis.

It should be noted that the data collection in the AE CRF is different from that of the e-diary:

- For redness, swelling, and fever, the measured size of redness and swelling at the injection site and temperature are recorded in the e-diary, but not in the AE CRF. As the missing e-diary entries are monitored with ongoing review of the prompted reactions reported in the AE CRF, any measurement recorded in the query response will be taken into consideration for the primary analysis using the data handling memo for analysis purposes. For the 7 days, only the maximum grading from both sources will be used for the aggregated severity analysis.
- For pain at the injection site and all other systemic events, the severity grading algorithm for the e-diary data and the AE CRF may not be the same. Pfizer will choose the highest-severity grade.

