## 3.1.1.2. Systemic Events Within 7 Days After Vaccination

Systemic events, including fever, fatigue/tiredness, headache, vomiting, diarrhea, muscle pain, and joint pain, are reported from Day 1 through Day 7 after vaccination, where Day 1 is the day of vaccination with RSVpreF or placebo. The derivations for the systemic events as described below will be handled similarly to the way that local reactions are handled for the presence for each participant, severity level, duration, onset day, and presence of systemic event on each and any day.

- 1. Presence (yes or no) of each systemic event on any day (Day 1 through Day 7) after vaccination.
- 2. Presence (yes or no) of any systemic event on any day (Day 1 through Day 7) after vaccination.

- 3. Maximum severity of each systemic event on any day (Day 1 through Day 7) after vaccination.
- 4. Maximum severity of any systemic event on any day (Day 1 through Day 7) after vaccination.
- 5. Duration of each systemic event after vaccination.
- 6. Onset day of each systemic event after vaccination.
- 7. Presence (yes or no) of each systemic event on each and any of the 7 days after vaccination.
- 8. Presence (yes or no) of any systemic event on each and any of the 7 days after vaccination.

The grading scale for systemic events is provided in the protocol. However, the derivation of severity of each systemic event on each day should be based on the maximum severity reported from the e-diary or AE CRF, if data are reported from both sources; or the e-diary alone if not reported from the AE CRF.

Fever is defined as a temperature of  $\geq 100.4^{\circ}\text{F}$  ( $\geq 38.0^{\circ}\text{C}$ ). The highest temperature for each day will be recorded in the e-diary. For reporting purposes, fever will be analyzed using the following temperature ranges:

- Mild ( $\geq$ 38.0 to 38.4°C from the e-diary or mild grade from the AE CRF);
- Moderate (>38.4 to 38.9°C from the e-diary or moderate grade from the AE CRF);
- Severe (>38.9 to 40.0°C from the e-diary or severe grade from the AE CRF);
- Grade 4 (>40.0°C from the e-diary or severe grade from the AE CRF, plus documented >40.0°C via CRF query or other sources).

If a participant reports a fever (or severity of fever) by accident, the correct temperature will be transcribed in a data handling memo to be included in the analysis, and the temperature that is confirmed as incorrect will not be included in the analysis.

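### Only fever has a replacement rule for e-diary entries confirmed as wrong; for the other nine prompted items, a true mild or moderate reaction can end up scored as no reaction

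*SAP*

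**What the plan says.** **Removal.** SAP 6.1.1.1 (main reactogenicity analysis) states that "e-diary data that are confirmed as errors will not be used for analysis". The same bullet imputes partly missing diary data as *no*.

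**Replacement, fever only.** SAP 3.1.1.2 provides that after a mistaken fever report "the correct temperature will be transcribed in a data handling memo to be included in the analysis".

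**Measurements from queries.** For redness, swelling and fever, SAP 3.1.1 says that "any measurement recorded in the query response will be taken into consideration for the primary analysis using the data handling memo". The sentence deals with missing diary entries, not wrong ones.

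**Second source.** When the diary and the AE CRF report the same event on the same day, "the highest grade from the 2 data sources will be used for that specific day for analysis" (SAP 3.1.1). Of diary reactions, Protocol 8.3.4 says: "These data do not need to be reported by the investigator in the CRF as AEs".

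**Blanks.** SAP 5.3.1.1 says that after AE CRF events are added, "all remaining missing days are considered as" *no*. It also says the diary does not let a question be skipped, so every item on a transferred day has a value. SAP 3.1.1.1.2 gives maximum severity 0 when the seven days are a mixture of missing and *no*.

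**How errors come to light.** Protocol 8.3.4.2, 8.3.4.3, 8.3.4.4 and 8.11 call for telephone contact after a Grade 3 or suspected Grade 4 report or high fever. A confirmed keying error is one of the listed reasons for not holding a site visit.

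**The concern.** The SAP treats one problem in two ways and gives no reason. A wrong temperature is corrected. A wrong grade for pain, headache or any of the other seven items is simply removed. A wrong grade is seldom a report of nothing: a parent who keyed severe may have meant moderate. Removing the entry loses the moderate reaction along with the mistake.

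The percentages of children with local reactions and with systemic events within 7 days are primary endpoints, shown by maximum severity in groups of about 20. The only reactogenicity sensitivity analysis (SAP 6.1.1.3) uses diary data without the AE CRF. It neither restores nor corrects a removed entry, so no planned output would show the effect.

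**Working it through.** The documents give no bias figure, entry-error rate or statistical basis for sample size (Protocol 9.5), so there is no stated number to reproduce. The check has three parts.

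**1. Following one entry through the rules.** A child has moderate injection-site pain on one day only. The parent keys severe, and the site telephones and confirms the mistake.

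- SAP 6.1.1.1: the severe entry is not used.
- SAP 3.1.1.2: the correction rule is for temperature, so it does not apply.
- SAP 3.1.1: the query-response route covers redness, swelling and fever measurements, for missing entries. Pain is outside it.
- AE CRF: SAP 5.3.1.1 expects entries there for missed diary days. This was not a missed day, and nothing requires an AE record.
- Protocol 8.11: the contact is recorded in source documents and the CRF, and an unscheduled visit has its own CRF page. The SAP names only the diary and the AE CRF as sources and does not say that this record replaces the entry.
- Result: the item is blank on that day and *no* on the other six. If the blank counts as missing, SAP 3.1.1.1.2 gives maximum severity 0.

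The last line is an inference. SAP 5.3.1.1 assumes that every item on a transferred day has a value, so it does not foresee a blank created by removing an error. At the least, the result is undefined.

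**2. One child in a group.** Inputs: n = 20 (20 per dose level at 2 to <5 years, and about 20 per risk group and dose level at 5 to <18 years; Protocol 4.1.1), with Clopper-Pearson 95% intervals (SAP 6.1.1.1).

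- Change per affected child: 1/20 = 5 percentage points.
- Example: 8/20 = 40% (19.1 to 63.9) becomes 7/20 = 35% (15.4 to 59.2).

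**3. Expected size under assumptions.** None of these rates is in the documents. Let *m* be the true mild/moderate rate for an item (10% to 50%), *s* the true severe rate (2% to 5%) and *u* the chance that a non-severe truth is keyed as Grade 3 (1% to 5%). Assume every such entry is confirmed and removed, the reaction occurred on one day only, and there is no AE CRF record.

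*Any-grade rate* after removal = m(1 − u) + s, a loss of m × u. With m = 30% and s = 5% the truth is 35%:

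| u | Loss (points) | Entry removed | Entry corrected |
|---|---|---|---|
| 1% | 0.3 | 34.7% | 35.0% |
| 3% | 0.9 | 34.1% | 35.0% |
| 5% | 1.5 | 33.5% | 35.0% |

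Over the whole range the loss runs from 10% × 1% = 0.1 point to 50% × 5% = 2.5 points.

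*Severe rate*, with s = 5%, u = 3% and no under-keying:

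- entries kept as keyed: s + (1 − s)u = 5% + 95% × 3% = 7.85%;
- false Grade 3 entries removed: 5.0%;
- false Grade 3 entries corrected: 5.0%.

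Removal and correction give the same severe rate, and both equal the truth.

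**The case against.** **The loss needs several things at once:** a mis-key to Grade 3, a true Grade 1 or 2, no report of that item on another day, and no AE CRF record. The study is descriptive with wide intervals. This is fair, and it is why the expected size is small. It does not supply the missing rule.

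**Other routes may recover the reaction.** AE CRF events are merged at the higher grade, which pushes rates upward, and the Protocol 8.3.4 sentence is most simply read as avoiding double entry of reactions already in the diary. That also stands. But none of these routes is required to carry the corrected grade of a removed entry into the analysis. The point concerns the direction of this one rule, not the net bias of all the rules together.

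**Three stronger readings are tempting, but the documents do not support them.**

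- *Severe rates are biased down.* Removing a Grade 3 that was truly lower is a correction, as part 3 of the working shows. The severe rate would suffer only where the removed entry's true value was itself severe.
- *Only high entries are ever checked.* The contact triggered by grade is one-sided, but Protocol 8.3.4 requires frequent online review of all diary data, 8.10.1 calls daily review optimal, 8.10.2 reviews the diary at Visit 2, and 8.12 requires contact when a diary is not being completed.
- *Dose decisions by the internal review committee are distorted.* Nothing says that SAP 6.1.1.1 governs those reviews; they run under a charter that is not part of these documents.

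**Conclusion.** The concern holds for any-grade and mild/moderate rates. A stated rule removes wrong entries for all ten prompted items, a stated replacement exists for one, and the most natural reading of the missing-data rules turns a true mild or moderate reaction into *no*. One such child shifts a rate by 5 points in a group of 20. Under the assumed rates, the average loss is 0.1 to 2.5 points per item. The true size is unknown because no entry-error rate is given, and it is probably small.

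The conclusion rests on a voided item being treated as missing, on the reaction appearing on no other day, and on there being no AE CRF record. It is still worth acting on: the endpoint is primary, the bias runs in one direction, and the SAP already contains the remedy for fever.

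**What to change.** In SAP 3.1.1 and 6.1.1.1:

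- Extend the fever rule to every prompted item. A diary entry confirmed as wrong is replaced by the grade or size that the investigator confirms, taken from the Protocol 8.11 contact or unscheduled-visit record and entered through the data handling memo.
- Score *no* for that item and day only when absence is confirmed, and state what happens when the true value cannot be established. One option is to leave it missing and show it as such.
- List every removed or changed entry by group, with the original and corrected values.

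A table of maximum severity with entries as originally keyed is optional. It would show the full effect of the corrections, but it would bring back some values known to be wrong.

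The cost is about two sentences in the SAP and one listing, plus a check that the record of a telephone contact captures the corrected grade or size. No clinical procedure changes.

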## 6.1.1.2. Supplementary Analysis

To support the assessment of reactogenicity, the endpoints below, as specified in Section 3.1.1.1 and Section 3.1.1.2, will be summarized per the supplemental analysis with the same analysis population:

- Duration (days) of each local reaction and each systemic event after vaccination.
- Onset day of each local reaction and each systemic event after vaccination.
- Presence of each and any local reaction and each and any systemic event, on each of the 7 days and for "any day (Days 1-7)."

The presentation of the results will include a basic descriptive summary without the 95% CIs for each group.

## 6.1.1.3. Sensitivity Analysis of Reactogenicity

Maximum severity of reactogenicity is also assessed using the e-diary data only. The difference between the primary analysis and this sensitivity analysis will also be presented.

#### 6.1.2. AEs, SAEs, and NDCMCs

AEs, SAEs, and NDCMCs will be summarized for each of the 6 age/risk/dose-level groups (Sections 2.2.1.1.2 through 2.2.1.1.4). Data will be summarized by vaccine group, according to the study interventions the participants actually received.

